10.2.1 Overview of Treatment-Emergent Adverse Events

An AE overview summary table will be prepared including the number of subjects reporting an AE, the percentage of subjects (%) with an AE, and the number of events (E) reported, for the following categories:

- Treatment-emergent adverse events
- Deaths
- Serious adverse events
- Adverse events leading to withdrawal
- Severe and life threatening adverse events
- Adverse drug reactions

10.2.2 Incidence of Treatment-Emergent Adverse Events

Treatment-emergent adverse events will be summarized in summary tables. The tables will display the total number of subjects reporting an AE and the percentage of subjects (%) with an AE. AEs will be presented alphabetically by system organ class (SOC) and in decreasing frequency of occurrence by preferred term (PT).

Summary tables will be prepared for:

- All adverse events
- Adverse events with an incidence [$\geq 5\%$] of subjects in any treatment group
- Adverse events by causality (related/unrelated)
- Adverse events leading to death
- Adverse events by intensity (mild/moderate/severe)
- Serious adverse events
- Adverse events leading to withdrawal

A supporting data listings will be provided for:

- All adverse events sorted by center, subject number, and date of onset
- Adverse drug reactions
- Adverse events leading to death
- Severe adverse events
- Serious adverse events
- Adverse events leading to withdrawal

Supporting data listing by SOC sorted alphabetically and PT sorted in decreasing frequency of occurrence will be provided for:

- All adverse events

The all adverse events table will summarize all the treatment-emergent AEs by SOC and Preferred Term displaying the total number of subjects (N) reporting an AE, the percentage of subjects (%) with an AE, and the number of events (E) reported will also be provided.

10.3 Chemistry and Hematology Laboratory Variables

Mean change and mean percentage (%) change from baseline at the end of trial will be presented for each laboratory variable. In addition, descriptive statistics, i.e., the number of subjects with data, mean, standard deviation, median, minimum, and maximum values, will be presented for observed values at screening and end of treatment for each laboratory variable.

Data listings will also be prepared by center for all subjects with any markedly abnormal laboratory safety values at any time-point (including screening/baseline) (appendix 1).

10.4 Vital Signs

10.4.1 Vital Signs

Baseline for all vital signs analyses will be the values obtained at the screening visit. The only planned post-baseline assessment of vital signs is at the End of trial visit.

10.4.2 Summary Statistics

Mean change and mean percentage (%) change from baseline at end of trial will be presented for each vital signs variable. In addition, descriptive statistics, i.e., the number of subjects with data, mean, standard deviation, median, minimum, and maximum values, will be presented for observed values and change from baseline at screening and end of treatment for each vital signs variable.

10.4.3 Data Listings

Data listings will be prepared by center for all subjects with any markedly abnormal vital signs value at any time-point (including screening/baseline) (appendix 1).

10.5 Other Safety Variables

10.5.1 OHSS

A summary table will be prepared showing the incidence and severity of early OHSS, late OHSS, and overall OHSS. This table will display the number and percentage of subjects (%) and the number of events. Early OHSS is defined as OHSS with onset ≤ 9 days after triggering of final follicular maturation. Note this includes OHSS with onset before triggering and OHSS with onset during stimulation where triggering is not performed.

10.5.2 Signs of Excessive Response

A table will be prepared summarizing signs of excessive response. The table will present the number of subjects in following categories:

- OHSS early onset defined as at most 9 days after hCG administration
- Cancellation of cycle due to excessive response
- Preventive action (leuprolide acetate)
- Received a medical or surgical intervention for OHSS

11 Interim analyses

No interim analysis is planned.

12 Deviations from protocol analysis

For some of the baseline characteristics, the analysis based on the safety population has been removed. The summaries based on mITT and PP populations were considered to be sufficient.

For the primary analysis, the sensitivity analysis based on ITT populations was removed. Furthermore, sub-group analysis by genetic testing was added.

For the primary analysis, it was added that patients that have positive pregnancy test at any time after the 8-9 week window post-fresh transfer will also be considered as positive for this primary endpoint.

13 References

14 Tables, Listings and Figures Shells

The document with tables, figures and listings (TLF) shells presented in a separate document.

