6.4 Visit 4 - Day Following Administration of Ovidrel®

The subject will return to the center (in the morning) the day following the Ovidrel[®] injection for P4 and E2 samples to be submitted to the central laboratory; serum hCG will be analyzed at the local lab. A TVUS will be performed. The date, time, and dosage of Ovidrel[®] will be recorded as well as study medication compliance. Adverse events and concomitant medications will be assessed and documented. Any symptoms of OHSS will be closely monitored.

The cycle will be cancelled in case of poor ovarian response (if the Investigator judges that ≥ 3 follicles of ≥ 17 mm cannot be reached after a minimum of 10 days of stimulation).

Subjects who have an excessive response to ovarian stimulation (>30 follicles of ≥12 mm and/or E2 ≥5000 pg/mL) will have the fresh transfer cancelled, and the hCG trigger will be replaced with a GnRH agonist trigger (4 mg leuprolide acetate). If leuprolide acetate is administered, a blood sample for LH will be collected and analyzed at the local lab. All resultant expanded blastocysts will be vitrified after trophectoderm biopsy, with no fresh blastocyst transfer in order to decrease the risk of OHSS. Following oocyte retrieval and blastocyst evaluation, an End of Trial (EOT) Visit will be scheduled or completed and the information will be documented in the eCRF.

In order to minimize the risk of empty follicle syndrome, the subject will return the morning after hCG trigger to draw serum hCG, E2, and P4 levels. If the hCG level is <50 IU/L and/or P4 is <3.5 ng/mL, then a booster/rescue second dose of hCG must be given on that day as soon as possible. If the subject received the GnRH agonist trigger, the bloods drawn will be LH, E2, and P4 levels. If, after the GnRH agonist trigger, the LH is <15 IU/L and/or the P4 <3.5 ng/mL, a rescue/booster dose of hCG (Ovidrel®) should be given as soon as possible. Delay of oocyte retrieval will be left to the clinician's discretion and will be based on the time at which the rescue dose was administered.

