6.8 End of Trial (EOT) Visit

EOT assessments will be performed at the subject's last scheduled visit. If the EOT visit cannot be scheduled on the same day as the last scheduled visit, it can be done the following day. In the case of premature discontinuation from the study, an EOT visit will be completed within 2 weeks after the subject's last scheduled visit.

A physical examination will be done and vital signs will be recorded. The following laboratory tests will be performed by a central laboratory (no AMH will be drawn):

- Serum chemistry: non-fasting glucose, blood urea nitrogen, creatinine, potassium, sodium, chloride, calcium, aspartate aminotransferase, alanine aminotransferase, and gamma-glutamyl transferase.
- Hematology: red blood cell count, white blood cell count, hematocrit, hemoglobin, platelet count, and differential count.

Adverse events and concomitant medications will be assessed and documented and drug accountability will be performed.

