- 4. Hemoconcentration is defined as hematocrit >45 %. Electrolyte disturbances are defined as hyponatremia (sodium <135 mEq/L) and/or hyperkalemia (potassium >5.0 mEq/L). Coagulation abnormalities are defined as presence of thromboembolic events, abnormal prothrombin time, or abnormal activated partial thrombin time. Diminished renal perfusion is defined as creatinine >1.2 mg/dL. Oliguria is defined as urine output less than 500 mL/24 hours. Anuria is defined as failure to produce urine. If applicable, actual volume of urine output will be recorded.

All cases of OHSS will be considered AEs and will be recorded in the source documents for that subject and on the AE page in the eCRF. Severe OHSS that requires medical or surgical intervention (i.e., paracentesis or hospitalization) is considered an SAE (see Section 8.4).

Early OHSS is defined as OHSS with onset ≤ 9 days after triggering of final follicular maturation. Classification of grade is according to Golan's classification system (Golan, 1989) and all OHSS cases will be graded as mild, moderate, or severe. Preventive interventions for early OHSS cover cycle cancellation due to excessive ovarian response, triggering of final follicular maturation with GnRH agonist, and administration of dopamine agonist (the latter is only considered as preventive intervention in subjects with ≥ 20 follicles of ≥ 12 mm).

Late OHSS is defined as OHSS with onset >9 days after triggering of final follicular maturation.

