- Frequency of ovarian hyperstimulation syndrome (OHSS) (early OHSS if the onset is ≤ 9 days after hCG administration and late OHSS if the onset is >9 days after hCG administration)

3 Trial design

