10.2 Adverse Events

Adverse events will be recorded from signed informed consent until the end-of-trial visit.

Adverse events (AEs) are classified according to the Medical Dictionary for Regulatory Activities (MedDRA) version 19.1 or later.

Missing values will be treated as missing, except for causality, intensity, seriousness, and outcome of AE. A ‘worst case’ approach will be used:

- if causality is missing, the AE will be regarded as related to the IMP
- if the intensity of an AE is missing, the AE will be regarded as severe
- if seriousness is missing, the AE will be regarded as serious
- if outcome is missing and no date of outcome is present, the outcome is regarded as ‘Not yet recovered’

Missing event start and event stop dates will be imputed in the most conservative way, i.e. the event should start as early as possible based on the (partially) missing start date while remaining treatment emergent (if relevant), and last as long as possible, i.e. until last visit or one day prior to the next event with the same preferred term, if any. In the latter case both consecutive AEs (with the same PT) will remain to be regarded as two separate events (despite being adjacent).

A treatment emergent adverse event is any adverse event occurring in the period from first administration of IMP till end-of-trial visit.

Pre-treatment adverse events will be reported in a listing only. This listing will be sorted by center and subject ID and date of onset.

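### SAP 10.5.2 and 2.2 date early OHSS from hCG administration while SAP 10.5.1 dates it from triggering, so adjacent safety tables can disagree for women with no hCG date

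*SAP*

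**What the plan says.** The documents use two starting points for the 9-day limit between early and late OHSS.

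- **From hCG.** The 10.5.2 table row reads "OHSS early onset defined as at most 9 days after hCG administration". The safety endpoints in SAP 2.2 use the same anchor for both halves, ending with "late OHSS if the onset is >9 days after hCG administration". The protocol's own endpoint list (2.2) is worded the same way.
- **From triggering.** SAP 10.5.1, which specifies the table of early, late and overall OHSS, puts the early limit at "9 days after triggering of final follicular maturation. Note this includes OHSS with onset before triggering"; the note goes on to include onset during stimulation when no trigger is given. Protocol 7.1.6 uses triggering for early OHSS and also for late: "Late OHSS is defined as OHSS with onset >9 days after triggering of final follicular maturation".

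Not every woman is triggered with hCG. For excessive responders (more than 30 follicles of at least 12 mm, and/or estradiol of at least 5000 pg/mL), protocol 6.4 says "the hCG trigger will be replaced with a GnRH agonist trigger (4 mg leuprolide acetate"). After an agonist trigger, hCG is given only as a rescue dose, if LH is below 15 IU/L and/or progesterone is below 3.5 ng/mL the next morning.

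**The concern.** Early and late OHSS frequency is a listed safety endpoint, and protocol 9.8.2 asks for the two to be tabulated separately. The population is selected for high response (AMH of at least 5 ng/mL), so agonist triggering is foreseen. The table in 10.5.2 describes excessive response, and leuprolide use is one of its four rows. Its early-OHSS row nevertheless depends on a date that a leuprolide-triggered woman without rescue hCG does not have. Two tables in consecutive SAP sections could then give different early-OHSS counts from the same data, with no stated reason.

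**Working it through.** The plan states no figure to reproduce. The check applies each rule, as written, to each type of woman. Day 0 is the day of trigger. The rescue dose is taken as day 1, because it follows the blood draw on the next morning. The onset days are examples.

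| Woman | Example onset | SAP 10.5.1 | SAP 10.5.2 early row |
|---|---|---|---|
| hCG trigger | day 5 | early (5 ≤ 9) | early (5 ≤ 9) |
| Leuprolide, no rescue hCG | day 5 | early (5 ≤ 9) | no hCG date, not counted |
| Leuprolide, rescue hCG on day 1 | day 10 | not early (10 > 9) | early (10 − 1 = 9 ≤ 9) |
| Never triggered | during stimulation | early, by the note | no hCG date, not counted |

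The rules agree in the first line and differ in the other three. The SAP 2.2 wording fails in the same way as 10.5.2 in the second and fourth lines.

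**Can hCG administration be read as any trigger?** Two places point against it. Protocol 7.1.6 names triggering with a GnRH agonist as one way of triggering final maturation, so triggering is the wider term. SAP 8.1.3 counts women given hCG and women whose hCG trigger was replaced as separate items.

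**How many women?** The documents give no rate for agonist triggering, rescue hCG or OHSS. As an illustration on assumed rates only, for agonist-triggered women without rescue:

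women per arm = 300 × g × (1 − r) × q

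Here 300 is the planned arm size, g is the proportion given the agonist (assumed 5 to 30%), r the proportion of those rescued with hCG (0 to 40%), and q the early-OHSS risk (0 to 5%).

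- Lowest: q = 0 gives 0.
- Middle: 300 × 0.15 × 0.80 × 0.02 = 0.72.
- Highest: 300 × 0.30 × 1 × 0.05 = 4.5.

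Women never triggered are not in this illustration.

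**Which half of the split is affected?** This part is inferred from the visit schedule. For agonist-triggered women, "Following oocyte retrieval and blastocyst evaluation, an End of Trial (EOT) Visit will be scheduled or completed". Retrieval is about 36 h after trigger (day 1.5) and blastocyst evaluation is 5 to 7 days later, so evaluation ends on day 6.5 to 8.5. Protocol 6.8 adds: "If the EOT visit cannot be scheduled on the same day as the last scheduled visit, it can be done the following day", which gives day 7.5 to 9.5. SAP 10.2 states: "Adverse events will be recorded from signed informed consent until the end-of-trial visit". If sites follow that timing, most OHSS recorded in these women would have onset by day 9, and the mismatch would fall mainly on the early row. If the visit is handled as premature discontinuation, with up to 14 further days, it could fall on day 20.5 to 22.5, and late cases could also be recorded.

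**The case against.** The best defence is that a workable definition already exists. SAP 10.5.1 specifies the main OHSS table and classifies agonist-triggered and untriggered women correctly. Protocol 7.1.6, in the protocol on which the SAP is based, agrees with it. A careful programmer might apply that rule throughout, and the table shells that would show this are in a separate document. This stands, and it limits the problem to one row of 10.5.2 and the wording of 2.2.

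It can also be said that hCG is loose shorthand for the trigger. In the protocol's Table 1, Visit 4 is headed as following the hCG dose, yet a footnote provides for LH at that visit if leuprolide was given. This makes the loose reading possible. It does not make it the stated rule, given SAP 8.1.3.

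Nor do the women disappear from 10.5.2. They appear in the leuprolide row. They may also appear in the row for cancelled cycles, because protocol 3.1.2 describes these cycles as cancelled and converted to freeze-all.

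A reader might infer more than the documents support:

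- **That late OHSS has no usable definition.** It is the natural complement of the early rule in 10.5.1, and protocol 7.1.6 states it outright.
- **That the documents fix the recording window for agonist-triggered women.** Protocol 6.4 and 6.8 set no day for the end-of-trial visit of a woman without a transfer. Protocol 8.5.2 also has serious events judged related to study drug reported after the last visit.
- **That no OHSS in agonist-triggered women can be placed in 10.5.2.** Those given rescue hCG have an hCG date.
- **That the SAP departed from the protocol without saying so in section 12.** The protocol contains the same split (2.2 against 7.1.6), so the SAP carried it over.

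**Conclusion.** The point holds as a minor inconsistency. Followed literally, the early row of SAP 10.5.2 omits early OHSS in leuprolide-triggered women without rescue hCG and in women never triggered, all of whom SAP 10.5.1 counts. It also moves the limit by about one day for women given rescue hCG. Confidence is high for the mismatch in the text and low for any number of women. The 0 to 4.5 per arm above rests wholly on assumed rates, and the true count could be zero.

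Only a few descriptive safety cells are affected. The primary analysis and the overall OHSS count do not change, and nothing in the documents supports a claim that the mismatch favours either arm. The conclusion assumes that the tables are programmed from the words of 10.5.2; if the shells already use triggering, only the SAP text needs correcting.

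**What to change.** In SAP 10.5.2 and SAP 2.2, replace the hCG anchor with the 10.5.1 definition: onset no more than 9 days after triggering, whether by hCG or GnRH agonist, including onset before triggering and onset during stimulation when no trigger is given. For clarity, add to 10.5.1 that late OHSS is onset more than 9 days after triggering, as in protocol 7.1.6. A line in SAP 12, saying that protocol 7.1.6 is followed rather than the wording of the protocol's endpoint list, is optional.

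The cost is a wording change in three places and a check that the table shells match. No new data are needed.

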Appendix 1 Markedly Abnormal Laboratory Safety Values and Vital Sign

Table 1: Markedly abnormal Criteria for Laboratory Tests

Variable	Units	Markedly abnormal Criteria	
		Low	High
Haematology			
Haemoglobin	g/L	≤ 115	Not applicable
Haematocrit	Ratio	≤ 0.37	≥ 0.56
Total WBC	10 ⁹ /L	≤ 2.8	≥ 16.0
Eosinophils	%	Not applicable	≥ 10
Neutrophils	%	≤ 15	≥ 90
Lymphocytes	%	≤ 10	≥ 80
Monocytes	%	Not applicable	≥ 20
Basophils	%	Not applicable	≥ 5
Bands	%	Not applicable	≥ 20
Platelets	10 ⁹ /L	≤ 75	≥ 700
Total RBC	10 ¹² /L	≤ 3.5	Not applicable
Clinical Chemistry			
AST	IU/L	Not applicable	> 3xULN
ALT	IU/L	Not applicable	> 3xULN
Alkaline phosphatase	IU/L	Not applicable	> 3xULN and 25% increase from baseline
GGT	IU/L	Not applicable	> 3xULN
LDH	IU/L	Not applicable	> 3xULN
Total bilirubin	μmol/L	Not applicable	≥ 1.5xULN
Urea nitrogen	mmol/L	Not applicable	≥ 10.7
Creatinine	μmol/L	Not applicable	≥ 177
Total protein	g/L	≤ 45	≥ 90
Albumin	g/L	≤ 25	≥ 65
Sodium	mmol/L	≤ 130	≥ 155
Potassium	mmol/L	≤ 3.0	≥ 5.8
Chloride	mmol/L	≤ 90	≥ 115
Phosphorus	mmol/L	≤ 0.5	≥ 1.9
Calcium	mmol/L	≤ 1.8	≥ 3.9
Uric acid	mmol/L	Not applicable	≥ 0.62
Glucose	mmol/L	≤ 2.8	≥ 10
Total cholesterol	mmol/L	Not applicable	≥ 8.0
Urinalysis: Quantitative			

Variable	Units	Markedly abnormal Criteria	
		Low	High
pH	None	≤ 4	Not applicable
Specific gravity	None	≤ 1.005	Not applicable
Urinalysis: Dipstick Chemistries			
Glucose	0 - 4+	Not applicable	Increase of 2 or more units from baseline
Casts		Not applicable	Increase of 2 or more units from baseline
Protein	0 - 4+	Not applicable	Increase of 2 or more units from baseline
Ketones	0 - 4+	Not applicable	Increase of 2 or more units from baseline
Blood (Hgb)	0 - 4+	Not applicable	Increase of 2 or more units from baseline
Urinalysis: Microscopic Variables			
RBC	no./hpf	Not applicable	≥ 10
WBC	no./hpf	Not applicable	≥ 20
Casts	no./hpf	Not applicable	Neg at baseline to positive on-treatment
Bacteria	no./hpf	Not applicable	Neg at baseline to positive on-treatment
Cells	no./hpf	Not applicable	Neg at baseline to positive on-treatment
Crystals	no./hpf	Not applicable	Neg at baseline to positive on-treatment

Table 2: Markedly abnormal Criteria for Vital Signs*

Variable	Criterion Value	Change from Baseline
Systolic blood pressure	≥ 180 mmHg	Increase of ≥ 20 mmHg
	≤ 90 mmHg	Decrease of ≥ 20 mmHg
Diastolic blood pressure	≥ 105 mmHg	Increase of ≥ 15 mmHg
	≤ 50 mmHg	Decrease of ≥ 15 mmHg
Pulse rate	≥ 120 bpm	Increase of ≥ 15 bpm
	≤ 50 bpm	Decrease of ≥ 15 bpm
Body weight	None	Increase of ≥ 7%
		Decrease of ≥ 7%

* To be identified as markedly abnormal, a treatment value must meet the criterion value and also the specified change from baseline.
